3.2.1 Primary Outcome Measures

23
24 There are three major areas of safety and tolerability that will be assessed in this phase I
25 trial. The outcome measurements will be compared between the two treatment groups
(Intervention v placebo) with intent to treat analysis.

26
27
28 **1. Evidence of invasive infection resulting from the administration of *L. reuteri* DSM
29 17938.** Baseline and daily temperature measurements will be made during the study
30 period. Complete hemogram with differential count obtained at baseline, on day 5, and
31 on day 28. Vital signs will be monitored daily during the administration of the treatment
32 (days 1-5). The evaluation of all febrile episodes will be done and include a physician
33 exam and the evaluation of blood smears for malaria and blood cultures for the
34 evaluation of possible bacteremia.

35
36 Specific outcome parameters in this category include:

37
38 a. Mean daily temperature
39 b. Incidence of fever on study days 1-5
40 c. Frequency of temperature readings categorized as fever (adjusted for number of
41 subjects per group)
42 d. Number of episodes of *L. reuteri* bacteremia

43
44 **2. Clinical tolerance.** The inclusion of a placebo group will allow for comparisons of daily
45 symptom measurements to be compared between the treatment and placebo group.
The symptoms will be monitored for at household visits, and will be graded as
adverse events according to defined criteria. Symptoms monitored as AEs include
fever, nausea/upset stomach, vomiting, diarrhea, irritability, rash, pruritis, and
wheezing or bronchospasm. Diagnostic microbiology will be performed on all stool
specimens from subjects who develop diarrhea during the 90 days following initiation
of therapy.

46
47 Specific outcome parameters in this category include:

- 1 a. Frequency and severity of symptoms monitored as AEs (adjusted for number of
2 subjects per group)
- 3 b. Frequency of all AEs (adjusted for number of subjects per group)
- 4 c. Frequency of SAEs (adjusted for number of subjects per group)

5

6

7 **3. Evidence of toxicity resulting from the *L. reuteri* DSM 17938 preparation.**

8 Participants will have baseline, day 5, and day 28 assessment of hematologic status and
9 renal and hepatic function. Assessment of renal function will include blood urea nitrogen
10 (BUN) and creatinine (Cr). Assessment of hepatic toxicity will include transaminases

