
10

11 **5.4.4 Handling of Withdrawals**

12

13

14 The study is voluntary and allows for the withdrawal of participation at any point in the
15 study. Despite this, we have a very low attrition rate in our studies. In general
16 withdrawal from the study is partial- most frequently related to blood draws. In all
17 cases, the reason for the withdrawal of consent will be discussed at length with
18 parents. We will ask that the parents of the participant to continue to allow visits to
19 monitor vital signs and illness history at the least. In most cases our experience
20 informs us that parents will allow stool collection to continue. Blood draws are the most
21 problematic- we will allow the family to opt for a fingerstick sample if the venous blood
22 draw experience is that which is underlying the withdrawal. We also would allow for
23 extended windows (i.e., blood draw at 35 days rather than 28 if the parent feels more
24 time between blood draws would allow for their continued complete monitoring,
25 although in this case a protocol deviation form would be included with the values. In
26 short, every attempt will be made to obtain the most complete safety and tolerability
27 data possible while respecting parental autonomy and their right to cease participation
28 in a voluntary study. No replacement of subjects is planned, and we expect the
29 number of consent withdrawals and missed study visits or missed study procedures to
30 be low.

31

32 **5.4.5 Termination of Study**

33

34

35 This study may be prematurely terminated if, in the opinion of the PI or sponsor there is
36 sufficient reasonable cause for termination. An example of a reason underlying
37 termination would be NIDDK concurrence with DSMB recommendation to end study
38 early, new findings that alter the safety profile of the product, discontinuation of study
39 product for active and matching placebo production or impending market
40 unavailability, the discovery of important protocol violations that may undermine the
41 integrity and conclusions of the study.

42 If the study is prematurely terminated or suspended, the sponsor will promptly inform

1 the investigators/institutions so that the investigators can inform the U.S. and Peruvian
2 regulatory authority(ies) of the termination or suspension and communicate the
3 reason(s) for the termination or suspension. The IRB/IEC will also be informed

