20 monitored AEs in Protocol Appendices C and E below) and unsolicited AEs on the diary
21 cards. Field workers will verify information recorded, determine and document the severity
22 of each AE recorded on the form, and assist with completing the card as needed. In the
23 event that the AEs in question are assessed to be of a more severe intensity than what is
24 recorded by the subject's parents, the diary card may be revised to reflect this
25 change. However, field workers will not "downgrade" any solicited or unsolicited adverse
26 events recorded by the parents. Parents of subjects will be instructed to contact the field
27 worker or study physician immediately if the enrolled child develops fever or becomes ill.
28 Subjects with AEs will be referred to the study physician, who evaluate the subject,
29 generate an AE report, and make an initial determination of association with study product
30 or not. AEs not listed in Appendices C, D, and E will be reported but not graded for
31 severity.

32 On day 5, when the final dose is administered, study personnel will collect a 3 ml. blood
33 sample for CBC, AST, ALT, total bilirubin, creatinine, and BUN. Out of range laboratory
34 values will be documented on the appropriate CRFs for laboratory values.

35 Temperature will be documented daily while receiving study intervention, and participants
36 with new onset of Grade 3 or 4 fever following initiation of intervention therapy (defined as
37 oral, axillary, or temporal temperature \geq 39.0 degrees C) and participants who appear
38 especially ill or toxic to the field worker will have a physician evaluation. In these cases,
39 blood will be examined in for malaria parasites by thick smear and a blood culture will be
40 performed. In the event of positive blood cultures, presumptive antibiotic treatment and
41 hospitalization (if deemed necessary by the attending physician) will be facilitated by
42 project personnel. Antibiotic therapy will be the standard pediatric doses of Ceftriaxone
43 and Gentamicin (for common causes of bacteremia from urinary and pulmonary sources)

1 with the addition of clindamycin if the study product is the suspected origin. Further details
2 on procedures for evaluating and empirically treating subjects with fever are found in the
3 section on Adverse Events, Bacteremia. Serious Adverse Events (SAEs) are defined in
4 Section 9.2.2, and any participant who develops an SAE, regardless of cause, will

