18 will be analyzed, except in the case that the physician or study team deems them to be
19 more severe than reported (the study team may upgrade, but NOT downgrade the
20 severity of the symptom).

21
22 Specific outcome parameters in this category include:

23
24 a. Frequency and severity of symptoms monitored as AEs (adjusted for number of
25 subjects per group)
26 b. Frequency of all AEs (adjusted for number of subjects per group)
27 c. Frequency of SAEs (adjusted for number of subjects per group)

28
29 All continuous variables will be summarized using descriptive statistics including number
30 (N), mean, standard deviation (SD), median, maximum, and minimum. All categorical
31 variables will be summarized using frequency counts and percentages.

32
33 Changes from baseline temperature and fever graded by defined toxicity categories will
34 be summarized using descriptive statistics by treatment group.

35
36 Concomitant medications, including those taken prior to study drug administration, will be
37 listed by subject. All concomitant medications taken after initiation of the study treatment
38 will be tabulated overall and by formulation. The number and percentage of subjects who
39 take at least 1 concomitant medication and the number and percent of subjects who take
40 each specific concomitant medication will be presented.

41
42 Treatment-emergent AEs will be defined as any event with a start date occurring on or
43 after treatment Day 1 or, if pre-existing, worsening after treatment Day 1. If a subject
44 reports the same AE more than once, then that subject will only be counted once for the

1 summary of that AE, using the most severe intensity.

2
3 Treatment-emergent AEs will be summarized as follows to the DSMB during closed
4 sessions:

5 • All treatment-emergent AEs;
6 • All treatment-emergent AEs by intensity;
7 • SAEs;
8 • All treatment-emergent SAEs by relationship to study drug; and
9 • AEs that led to premature discontinuation of study drug.

10 All SAEs and AEs leading to premature withdrawal from the study will be listed.

11
12 Hematology and blood chemistry parameters will be summarized at baseline and at the
13 end of the study. Laboratory values and changes from baseline in laboratory values will
14 be summarized descriptively for all subjects and by treatment group. A summary of shifts
15 from baseline to final evaluation will be given for each parameter for all subjects and by

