16 treatment group. The normal range for each parameter will be used to create categories
17 of low, normal, or high. Any result higher than the upper limit normal (ULN) will be
18 categorized as high, any result lower than the lower limit of normal (LLN) will be
19 categorized as low, and any result within the LLN and ULN will be categorized as normal.
20 The number and percentage of subjects in each shift category from baseline to final
21 evaluation will be shown for each parameter. Only the hematology and blood chemistry
22 tests with a numeric normal range and at least one follow-up value will be analyzed for
23 shifts from baseline. The number and percentage of subjects with clinically significant
24 values will be presented.

25
26 **B. The secondary outcome measurements** are

27
28 1. To determine the duration of shedding of *L. reuteri* DSM 17938 following controlled
29 administration.

30
31 Since the longitudinal nature of the repeated PCR assays results in correlated outcomes,
32 generalized estimating equations (GEE) will be used to model the binary response
33 whether subjects exhibited a positive PCR result during the various period of study. The
34 duration of shedding of *L. reuteri* will be assessed using Kaplan Meier Product limit
35 estimates.

36
37
38
39
40 **11.2 Sample Size Considerations**

1
2
3 The sample size for this Phase 1 safety trial in healthy children aged 2-24 months is
4 determined by historical precedent for safety in human use.

5
6 Enrollment for the prior Phase 1 studies in adults (Safety of LR in Healthy volunteers
7 #NCT00774163) and children (Safety of LR in healthy children 2 to 5 years of age in Peru
8 #NCT02124122) have been able to recruit and retain >95 subject (Phase 1 child study in
9 progress). We have high and similar rates of retention in our other studies with more
10 complexity and participant burden, even among our birth cohorts.³⁷

11
12 Missing data will not be imputed. Data will be analyzed per treatment group assignment
13 after the administration of a single dose of product for all safety and tolerability analyses.
14 Data regarding the duration of carriage will be restricted to those individuals who complete
15 5 days of therapy.

16
17 The amount of subjects in this study will likely be underpowered to detect differences in
18 most secondary outcomes. This is in part due to the lack of information on key

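### The laboratory shift table runs only to an undefined final evaluation, so no stated table isolates the Day 5 end-of-dosing panel by arm

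*Combined protocol and SAP*

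**What the plan says.** Section 3.2.1 (primary outcome area 3, toxicity) sets the schedule: "Participants will have baseline, day 5, and day 28 assessment of hematologic status and" renal and hepatic function. Section 7.4 places the first follow-up panel at the end of dosing: "On day 5, when the final dose is administered, study personnel will collect a 3 ml. blood" sample. Appendix A schedules no panel after Day 28, although participation runs to Day 90.

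The analysis text is in Section 11.1. It opens with "Hematology and blood chemistry parameters will be summarized at baseline and at the" and runs on "end of the study. Laboratory values and changes from baseline in laboratory values will" be summarized descriptively, overall and by treatment group. The second of these sentences names no visit. The shift summary does name its end points: shifts "from baseline to final evaluation will be given for each parameter for all subjects and by" treatment group. The display is "The number and percentage of subjects in each shift category from baseline to final" evaluation, in categories of low, normal and high. On eligibility for that table, only "tests with a numeric normal range and at least one follow-up value will be analyzed for" shifts.

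Neither end of the study nor final evaluation is defined for the laboratory data.

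**The concern.** Day 5 is the only panel taken during or at the end of dosing. A table that compares baseline with the last value cannot show a change that appears by Day 5 and has gone by Day 28. For a five-day product given to infants, a reader of the safety report will want that display by arm, and the plan does not specify it.

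Two matters of wording add to this. Section 7.5, in discussing iron supplementation, refers to clinical and laboratory outcomes by group at days 5 and 28, which sits uneasily with a summary at baseline and end of study only. And because final evaluation is undefined, it is unclear what happens to a child with a Day 5 panel but no Day 28 panel. Section 5.4.4 says that "withdrawal from the study is partial- most frequently related to blood draws. In all" cases the reason will be discussed with the parents, so the situation is foreseeable even though few cases are expected.

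**Working it through.** The plan gives no figure to reproduce: the sample size rests on historical precedent, and no laboratory effect size or rate is stated. The check is one of table logic, with an illustration.

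**1. Timing.** Last dose Day 5, last panel Day 28: 28 − 5 = 23 days.

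**2. What enters the shift table.** With complete sampling, 60 children × 2 follow-up panels = 120 post-baseline panels. If final evaluation means Day 28, 60 enter the shift table and the 60 Day 5 panels do not. This count applies to the shift table only, because the sentence on values and changes from baseline sets no visit limit.

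**3. How a transient change is classed.** Exclusion criterion 9 requires normal leucocyte count, BUN, creatinine, AST, ALT and bilirubin at entry. For these six tests, abnormal on Day 5 and normal on Day 28 is tabulated as normal to normal. Hemoglobin differs, since Section 7.3 excludes only severe anemia.

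**4. Single-child illustration.** Assume baseline ALT 30, Day 5 ALT 156 (3 × the Appendix D limit of 52) and exponential recovery with half-time h days. Day 28 ALT = 30 + (156 − 30) × 2^(−23/h):
- h = 3: 30.6
- h = 5: 35.2
- h = 7: 42.9

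All are below 52, so the shift table shows normal to normal. By Appendix D, 156 is Grade 1 (53–200), so Section 9.2.4 would have it reported as an AE.

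**5. Group illustration.** Allocation 2:1 gives 60 × 2/3 = 40 active and 60 × 1/3 = 20 placebo. The Day 5 out-of-range rate p and the share resolved by Day 28 are assumptions. Expected number = 40p; chance of at least one = 1 − (1 − p)^40.

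| p | Expected active children out of range on Day 5 | Chance of at least one | In baseline-to-Day 28 shift table: all resolve / half resolve |
|---|---|---|---|
| 5% | 2 | 87.1% | 0 / 1 |
| 10% | 4 | 98.5% | 0 / 2 |
| 20% | 8 | >99.9% | 0 / 4 |

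A baseline-to-Day 5 or baseline-to-worst shift table would show all 2, 4 or 8.

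**6. What else would catch the value.**
- *Appendix D tests:* mean values (3a) and out-of-range frequency (3b) have no visit limit. Grades 1–2 are reported as AEs and Grades 3–4 as SAEs (Section 9.2.4). The DSMB closed report gives out-of-range values by arm (Section 9.6).
- *Low white count:* Appendix D gives a normal range of 6,000–17,500 but grades only values above 17,500. A low value counts as out of range under 3b but has no toxicity grade, and 3b as worded does not separate low from high.
- *Neutrophils and platelets:* Section 11.1 names absolute neutrophil count as a measure of hematologic status, but Section 9.2.4 lists the differential and platelets as non-monitored and Appendix D omits both. They fall outside 3a and 3b, so the Section 11.1 summary and shift tables are their main planned display. Their baseline need not be normal, so a simple count could not replace a shift table.
- *Hemoglobin:* under Section 7.5, iron for low values starts at least 5 days after the last dose, so Day 28 may be on iron while Day 5 precedes it.

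**The case against.** The strongest reply is that Day 5 is not left out of the laboratory analysis. Outcomes 3a and 3b sit directly under the baseline, Day 5 and Day 28 schedule. Changes from baseline and the count of clinically significant values carry no visit limit. Section 7.5 shows that a Day 5 comparison by group is intended. Graded values reach AE/SAE reporting and the DSMB, and the ALT example above would be caught. For the six tests that must be normal at entry, any out-of-range Day 5 value is already a change from normal, so 3b carries much of what a Day 5 shift table would.

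This stands, and it rules out a stronger reading that a reader might infer: that the plan shows only the recovered value and cannot answer the toxicity objective. It does not remove the narrower gap. None of these routes names a visit, so a count pooled over Day 5 and Day 28 need not separate an excess at end of dosing from a later one. The argument from normal entry values does not extend to hemoglobin, neutrophils or platelets.

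A reader might also infer that the shift table will mix Day 5 and Day 28 values. The documents leave this open but do not establish it. The requirement for one follow-up value is worded about tests, not children; Section 11.2 says missing data will not be imputed; and Section 5.4.4 offers a fingerstick or a later draw to keep the sample.

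Nor do the documents show that toxicity is most likely on Day 5. Section 2.2 describes live cells that multiply and colonize, and stool PCR runs to Day 36, so Day 28 is also a relevant safety time point. The case is for showing both visits.

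**Conclusion.** The point holds as a defect in the specified tables. As written, the shift table shows none of the Day 5 abnormalities that resolve by Day 28: 0 of an expected 2, 4 or 8 active children at assumed rates of 5%, 10% or 20% with full resolution, and 1, 2 or 4 if half resolve. This rests on reading final evaluation as Day 28 and on assumed rates, since the plan gives none.

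For Appendix D tests the consequence is loss of a clear by-visit display by arm, not loss of the signal. It is more serious for neutrophils and platelets, and for a low white count, where the fallback routes are absent or weaker. Because toxicity is a primary outcome area and the samples are already planned, the tables should be corrected before the database is locked.

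**What to change.** In Section 11.1, replace the laboratory summary and shift text with the following:

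- Values and changes from baseline summarized at Day 5 and at Day 28 separately, by arm and overall.
- Shift tables by arm from baseline to Day 5, baseline to Day 28, and baseline to worst post-baseline value. Use low/normal/high for every parameter, including absolute neutrophil count and platelets, with their reference ranges stated. Add Appendix D grade where one exists. For tests with limits on both sides, show worst low and worst high separately.
- Out-of-range frequency (3b) reported by visit, and by direction where both limits exist.
- Final evaluation replaced by Day 28, with a missing Day 28 shown as missing. State how a late draw allowed under Section 5.4.4 is placed.
- Sections 7.5 and 11.1 reconciled on the visits analyzed.

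The cost is revised wording and a few more descriptive tables. No new samples, visits or children are needed.

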3.2.2 Secondary Outcome Measures

Secondary outcomes are restricted to:

1) The assessment of the duration of shedding of *Lactobacillus reuteri* (Lr) strain DSM 17938 following administration. This will be determined by an endpoint PCR assay for *L. reuteri* done on stool collected on D3, D5, D12, D15, D18, D24, D28, D36 on all participants.

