5 STUDY ENROLLMENT AND WITHDRAWAL

1

2 **5.1 Subject Inclusion Criteria**

3

4

5 In order to be eligible to participate in this study, a subject must meet all of the following
6 criteria:

7

- 8 • Have a parental permission form signed by both parents
- 9 • Be between 8 weeks to 24 months of age with no preexisting exclusion criteria
- 10 • Have parents who are willing to comply with all planned study procedures and be available for planned study visits for 3 months.

1
2 **5.2 Subject Exclusion Criteria**

3
4 1) No enrollment of family members in households where any of the following are
5 present:
6
7 a. Another study participant in the household
8
9 b. Presence of immune suppressed individuals or use of immunosuppressive
10 agents (including but not limited to corticosteroids, methotrexate, etc.) by any
11 household member
12
13 c. Presence of a serious congenital anomaly or chronic medical condition that in
14 the opinion of the investigators would contraindicate participation in any household
15 member, including history of gastrointestinal surgery, chronic gastrointestinal
16 illness, abnormal intestinal anatomy, or abnormal bowel functionality
17

18 The following risk factors are at the level of the individual child:

19
20 2) Allergy to penicillin, cephalosporins, clindamycin or gentamicin
21 3) History of antibiotic use in the last 30 days
22 4) Use of probiotic products within the past 30 days, including masato (local
23 product with fermenting bacteria) and yogurt products containing live
24 bacterial cultures.
25 5) History of diarrheal illness within the past 30 days (See definition in Protocol
26 Appendix B)
27 6) Presence of fever or a pre-existing adverse event monitored in the study
28 (See Protocol Appendix B Definitions of AEs for specific adverse events
29 monitored in the study)
30 7) Positive results on serum diagnostic tests for antibodies to HIV.
31
32 8) Presence of severe anemia, defined as serum hemoglobin \leq 7 gm/dL
33
34 9) Out of range laboratory values for total leucocyte count, BUN, Creatinine,
35 AST, ALT, and total bilirubin monitored as potential adverse events, as
36 described in Appendix E.
37 10) Pre-enrollment stool sample (collected within 14 days of day 1 of the study)
38 is positive for *L. reuteri* by PCR.
39
40

1 **5.3 Strategies for Recruitment and Retention**

2 The community where recruitment will occur has been a research site for the current

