6.5 Assessment of Subject Compliance with Study Intervention/Investigational Product

All treatments are directly administered by study staff. Missed dosages will be documented. In the case that a subject is not available on a study day a 1 day window will be tolerated for the administration of a single missing dose. The daily dose is restricted to a single dose per day, so in this case, the dosing interval would occur over a 6 day period. Follow-up schedule would not be altered from the programmed plan. No more than a single dose will be given this window- if a second dose were to be missed, it would be documented in a protocol deviation form and analyzed per group treatment assignment. Subsequent doses are done at 24 hour intervals from the last dose, but visit scheduling cannot be altered after the first dose is administered.

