19 parameters needed for sample size calculations. For example, in this age and context, to
20 calculate the duration of *L. reuteri* carriage following administration it is not known how
21 many subjects will become positive for *L. reuteri* by PCR following administration.
22 Similarly, it is not known how frequent intermittent passage of *L. reuteri* positive stool is in
23 individuals in this community, although about 10% of individuals in this age range test
24 positive. This data collected as part of this Phase 1 study will provide important
25 information of use in subsequent phase 2 trial [Efficacy of *Lactobacillus reuteri* in healthy children aged
26 2-24 months in the treatment of environmental enteropathy] .

27

1
2
3
4 11.3 Planned Interim Analyses (if applicable)
5

6 No formal interim analyses are planned; however, accumulated phase 1 trial data will be
7 reviewed by treatment group every 3 months by the NIDDK and DSMB.
8
9

10 **11.3.1 Safety Review**
11
12

13 Subject accrual, status adherence data on visits and intervention, adverse events and
14 rates of adverse events will be reported to the DSMB every three months. SAEs will be
15 reported within 24 hours of occurrence. Details of the interval reports are specified in
16 the DSMP.
17

18 The study would be halted if two or more subjects develop a similar SAE for which the
19 relationship to the study product cannot be excluded. This would include, but not be
20 limited to bacteremia with the product strain.
21

22 Individuals with a SAE during the period of probiotic administration will have the
23 intervention stopped regardless of the determined relationship to the study product, but
24 follow-up monitoring visits and testing would be completed to the greatest extent
25 possible, and the SAE would be managed until resolved.
26

27 INS requests SAE reporting, annual reports, and study termination report. Annual
28 reporting to IRB is planned for Tulane, Johns Hopkins University and AB PRISMA.
29
30

1
2
3

5

6 **12 SOURCE DOCUMENTS AND ACCESS TO SOURCE 7 DATA/DOCUMENTS**

8

9 All participants will have a chart composed of a copy of the signed consent document, all
10 CRFs, clinical laboratory values (CBC, AST, ALT, BUN, Creatinine, and total bilirubin
11 and screening day 0 *L. reuteri* PCR status, but not subsequent Lr PCR tests), diagnostic
12 testing results performed as part of adverse event evaluations, and copies of hospital

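### Shedding duration is planned as a plain Kaplan-Meier estimate although stools 3 to 8 days apart only bracket its end, and no event rule or time origin is stated

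*Combined protocol and SAP*

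**What the plan says.** Section 3.2.2 names one secondary outcome, the duration of shedding after administration, by PCR "done on stool collected on D3, D5, D12, D15, D18, D24, D28, D36 on all" participants. For its analysis, section 11.1 B gives two methods. A GEE models "whether subjects exhibited a positive PCR result during the various period of study", and the duration "will be assessed using Kaplan Meier Product limit" estimates.

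Other provisions that bear on this:

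- **Analysis set (11.2).** "Data regarding the duration of carriage will be restricted to those individuals who complete" 5 days of therapy. Missing data are not imputed.
- **Dosing (6.5).** If one dose is missed, "the dosing interval would occur over a 6 day period. Follow-up schedule would not be altered from the programmed plan".
- **Stool window (Appendix A).** A stool may be up to 48 hours off schedule, after which it counts as missing.
- **Unknowns (11.2).** The plan does not know how "many subjects will become positive for" *L. reuteri*, and "it is not known how frequent intermittent passage of" positive stool is. It puts positivity in this age range at about 10%.
- **Screening (5.2, criterion 10).** "Pre-enrollment stool sample (collected within 14 days of day 1 of the study") must not be PCR-positive.

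The documents do not say what ends shedding (first negative, last positive or confirmed negative) or which dose starts the clock. They give no rule for a child still positive at D36, never positive, or positive again after a negative. Interval censoring is not mentioned.

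**The concern.** Kaplan-Meier needs an event date for each child. Here a child who clears is known only to have done so between two stools, so the analyst must supply a date, and the text allows several. Each choice moves the median, and the choice could be made after the results are seen.

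The origin is equally open. Doses are given on days 1 to 5, so counting from the first or the last dose shifts every duration by 4 days. Section 7.5 also labels the first-dose day as day 0, where Appendix A calls it Day 1. If dosing runs to a sixth day while visits stay fixed, the D5 stool precedes the last dose and cannot mark the end of shedding.

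Section 11.2 says that these data will inform the next trial, so a duration that is wrong by several days would be carried forward.

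**Working it through.** The plan states no figure for shedding duration, so there is none to reproduce.

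**Inputs.** Stool days are from 3.2.2. Sixty children randomized 2:1 give 60 × 2/3 = 40 active. The true median is not in the documents, so it is varied as an assumption.

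**Step 1: gaps from D5, the planned last-dose day.** 12−5 = 7; 15−12 = 3; 18−15 = 3; 24−18 = 6; 28−24 = 4; 36−28 = 8. If the 48-hour window is read as either side of the nominal day, the widest possible gap is 8 + 4 = 12 days. A missing D24 stool would join two gaps: 6 + 4 = 10 days.

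**Step 2: large-sample error.** Let the true median *m* lie between consecutive stools *L* and *R*. First-negative dating puts the median at *R*, late by *R − m*. Last-positive dating puts it at *L*, early by *m − L*. The two errors add up to the gap.

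- Day 6: 12−6 = 6 late, 6−5 = 1 early.
- Day 8: 12−8 = 4 late, 8−5 = 3 early.
- Day 11: 12−11 = 1 late, 11−5 = 6 early.
- Averaged within a gap, each error is half its width: 3/2 = 1.5 to 8/2 = 4 days.
- Averaged over D5 to D36: (49+9+9+36+16+64) / (2 × 31) = 183/62 ≈ 3.0 days each way.

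**Step 3: simulation with 40 children.** Assumptions: exponential durations, nominal days, complete stools, uninterrupted shedding, no background positivity. Entries are mean estimated medians (study day).

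| True median | 8 | 12 | 15 | 20 | 24 |
|---|---|---|---|---|---|
| Kaplan-Meier, first negative | 12.0 | 13.5 | 16.6 | 22.4 | 26.5 |
| Kaplan-Meier, last positive | 5.0 | 8.4 | 13.0 | 17.6 | 21.0 |
| Kaplan-Meier, midpoint | 8.5 | 10.7 | 14.7 | 20.0 | 24.1 |
| Interval-censored Weibull | 8.2 | 12.1 | 15.2 | 20.2 | 24.4 |

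At true day 20 the visit-day rules are about 2.5 days late or early. Outside the tabulated medians the error can be larger: 6.0 days late at day 6, 5.0 late at day 7, and 4.8 early at day 10. At day 6 the midpoint rule gives 8.5, which is 2.5 late.

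**Step 4: missed positives.** Here 10% of stools during shedding are assumed to read negative.

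| True median | 8 | 12 | 15 | 20 | 24 |
|---|---|---|---|---|---|
| Kaplan-Meier, first negative | 12.0 | 12.6 | 14.5 | 17.0 | 18.8 |
| Weibull, one negative | 8.2 | 11.0 | 13.0 | 15.8 | 17.6 |
| Weibull, two negatives | 8.1 | 11.8 | 14.5 | 19.3 | 23.0 |

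From day 12 on, the one-negative Weibull is further from the truth than first-negative Kaplan-Meier. A repeat run gave 15.6 against 16.8 at true day 20.

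**Step 5: background positives.** With an assumed 10% per stool (exponential), the Weibull medians are 9.3 / 13.0 / 15.8 / 21.2 / 25.3, which is 0.8 to 1.3 days late. The corresponding first-negative medians are 12.0 / 14.3 / 17.0 / 23.0 / 27.3.

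**Step 6: precision.** On nominal days the single gap reported by the Turnbull estimate contained the true median in 100, 97, 85, 54 and 78% of trials at days 8, 12, 15, 20 and 24. A bootstrap 95% interval contained it in 99 to 100%. Those intervals were about 7, 12 and 16 days wide at days 8, 12 and 15. At days 20 and 24 they were about 19 and 20 days wide when cut off at D36, with 4% and 31% open-ended beyond it.

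**The case against.** The strongest reply is that the plan leaves the event date open and is not thereby biased. Midpoint dating fits the text and, at the five tabulated medians, errs by at most 1.3 days. This stands. A reader might infer that the stated method necessarily gives a duration wrong by days; the documents do not support that, because they fix no event rule. The midpoint is not always safe either: its large-sample error can reach half a gap, 1.5 to 4 days.

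A second reply is that a simple interval-censored analysis is not uniformly better. This also stands. The Weibull median was closer than first-negative Kaplan-Meier in all 30 scenarios simulated without missed positives (two distributions, three background rates, five medians), but not when positives are missed. Section 11.2 says the frequency of intermittent passage is unknown, so neither situation can be assumed.

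A third reply is that this is a descriptive secondary outcome in a Phase 1 safety trial, that 11.2 itself expects low power for most secondary outcomes, and that the GEE needs no event date. That limits the weight of the point. It does not answer it, because the GEE describes positivity and supplies no duration.

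**Conclusion.** The concern holds as a modest one. The end of shedding is interval-censored, the planned estimator does not allow for that, and neither event rule nor origin is stated. With visit-day dating the median is late or early by near 0 up to the full gap (3 to 8 days), on average about half a gap. The choice of origin adds 4 days. These sizes assume nominal days, complete stools and uninterrupted shedding.

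A reader of the first table might take about 1 to 4 days late or 2 to 4 days early as the general range. It applies only to those assumed medians; days 6, 7, 10 and 11 fall outside it. Nor can the 10% positivity in 11.2 be read as the background rate in enrolled children, since criterion 10 removes those who test positive at screening; that rate is unknown.

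The primary safety conclusions do not depend on any of this.

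**What to change.** In 11.1 B, replace the Kaplan-Meier sentence with text to this effect:

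> Shedding duration is measured from the actual last dose, using actual collection dates, in active-arm children who complete 5 doses. Only stools collected after the last dose define its end. The end is interval-censored between the last positive stool (or the last dose, if later) and the first post-dose negative. Children still positive at their last stool are right-censored there. Never-positive children are reported as a proportion. The curve is the Turnbull estimate; the median is given as the gap in which it falls, with a bootstrap 95% interval. A Weibull interval-censored median is supportive. Results are reported side by side for two definitions of the end: the first negative, and two consecutive negatives, with a single negative at the final stool kept as an upper bound. Later positives are listed against placebo-arm positivity on the same days.

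The two definitions need equal standing, because a large difference between them points to intermittent shedding or missed positives. The bootstrap interval is needed because the gap alone is not a confidence statement.

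The cost is SAP wording and standard software, with no extra visits or samples. The SAP should state the downsides:

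- intervals are wide and may be open-ended past D36 at later medians;
- a median inside D5 to D12 cannot be located further without a distributional assumption;
- high background positivity biases the result upward;
- if positives are missed, the one-negative estimate is early and can be further from the truth than first-negative Kaplan-Meier.

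If the sponsor keeps Kaplan-Meier, the event date, origin and censoring rule should still be fixed before unblinding.
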